10.2.4 Patient Identification and Randomization

Each patient will be assigned a unique patient identification number. Upon signing of the ICF, subjects will be assigned an ID composed of a two digit site number and a two digit subject number (e.g. site 1 subject 1 would be assigned 01-01). Screen failures that are allowed to be re-screend will keep the same site assigned ID. There are no plans to replace subjects that drop out of the study.

 Catalyst pharmaceuticals	CMS-001 Version Amendment 5	Page 44
--	--------------------------------	---------

Randomization will be across sites to maintain the 1:1 ratio of drug:placebo assignment. The assignments to treatment (amifampridine phosphate or placebo) will be based on a computer-generated randomization code. A central point of contact will be provided to the site pharmacist to obtain the treatment sequence for the subject to be enrolled in Period 1 on the last day of the run-in period (Day 0).

10.2.5 Re-screening

Re-screening of screen failures will be allowed, if re-screening is approved by the Medical Monitor. Justification of the reason for re-screening must be clearly stated in the patient's source documentation. No new consent would be required if re-screened within 30 days.

10.3 Treatments

10.3.1 Treatments Administered

Catalyst or its designee will provide the study site with a supply of IP sufficient for the completion of the study.

Investigational product: Amifampridine phosphate tablets 10 mg will be provided in round, white-scored tablets, and containing amifampridine phosphate formulated to be the equivalent of 10 mg amifampridine base per tablet. The product will be provided to the pharmacy department, who will dispense the necessary amount for each part of the study.

[figure not shown]
Placebo: A placebo equivalent will be provided as tablets indistinguishable from the amifampridine phosphate tablets. The placebo will be administered consistent with the dose regimen of amifampridine phosphate.

10.3.2 Identity of Investigational Product

The chemical name of amifampridine phosphate is:

- 3,4-pyridinediamine, phosphate (1:1) diamino-3,4-pyridine, phosphate salt
- 3,4-diaminopyridine phosphate

The chemical structure is provided in [Figure 1](#).

Figure 1. Chemical Structure of Amifampridine Phosphate

10.3.2.1 Product Characteristics and Labeling

Drug product is formulated as a phosphate salt of amifampridine. Tablets were developed to provide the equivalent of 10 mg of amifampridine base for oral administration. Each tablet contains amifampridine phosphate, microcrystalline cellulose, colloidal anhydrous silica, and calcium stearate. The bottles of tablets are labeled “Amifampridine phosphate Tablets, 10 mg.”

The tablets are to be dispensed by the site pharmacy department into suitably sized pharmacy bottles for patient use. Placebo will be provided as tablets indistinguishable from amifampridine phosphate. The amifampridine phosphate tablets and placebo tablets will be clearly labeled and the pharmacist is responsible for dispensing the amifampridine phosphate tablets or placebo tablets, as needed, for each patient.

Each bottle will be labeled to include the compound name, site number, patient ID number, date dispensed, storage instructions, the statement ‘Caution – New Drug – Limited by Federal law to investigational use,’ trial number, manufacturer name and address, and area for instructions for use.

10.3.2.2 Storage

At the study site, all IP must be stored at room temperature (20-25 degrees Celsius) and in a secure area accessible only to the designated pharmacist and clinical site personnel. All IP must be stored and inventoried, and the inventories must be carefully and accurately documented according to applicable national and local regulations, ICH GCP, and study procedures.

10.3.3 Directions for Administration

All doses of study treatment will be taken at home, except during the in-clinic study visit. If the patient takes the IP two or more times a day, then the patient should be given specific instructions on dosing relative to the time of their clinic visit to assure a dose will be given

during the in-clinic visits. A dose must be administered in the clinic in order to facilitate efficacy assessments. All safety assessments (vital signs, laboratory tests) are to be performed before the dose administered to the patient during the scheduled in-clinic visit. All efficacy assessments will be performed at standardized times relative to the dose administered in the clinic. In this case, the dose will be 40 minutes before the first efficacy assessment.

Assessment	Start Time After Dose* (\pm 10 minutes unless otherwise specified)
SGI	40 minutes
MFM 20 or 32	after SGI
Simulated Single fiber EMG [^]	after SGI
Slurp test [^] , CGI-S and CGI-I	At end of assessments

*Administration of medication represents Time 0 (minutes)

[^]Optional test

If the stimulated single fiber EMG (optional assessment) is not to be performed, then the slurp test (also optional), CGI-S and CGI-I assessments should be done following completion of the MFM.

The dose of amifampridine phosphate will be individually determined by the investigator, within the bounds of a total daily dose of 10 mg to 80 mg, divided into doses taken 2 to 4 times per day generally taken with food (e.g. breakfast, lunch, dinner, and snack before bed) as prescribed by the investigator, based on optimal neuromuscular benefit (see [Table 4](#)).

All doses of study medication will be taken orally by mouth, with the following exceptions:

- children unable to swallow tablets will have the tablets crushed and mixed with a small amount of food; and
- children with a nasogastric or gastrostomy tube will have the tablets crushed and diluted in 5 to 10 mL of water and given through the tube.

Table 4. Dosing Guidelines

	Children^a		
	Ages up to 3 Years	Ages 3 to 16 Years	Ages >16 years
Recommended starting dose	1 mg/kg/day, 3 times per day (to a maximum of 5 mg, 3 times a day)	5 mg, 3 times per day (15 mg/day total)	10 mg, 3 times per day (30 mg/ day total)
Initial dose escalation	May increase dose to 1 mg/kg, 4 times per day	May increase dose to 10 mg, 3 times per day (30 mg/day total)	May increase dose to 10 mg, 4 times per day (40 mg/day total)
Subsequent dose escalations	May increase dose by 1 mg/kg/day to the maximum daily dose of 60 mg/day	May increase dose to 10 mg, 4 times per day (40 mg/day total) May continue to titrate dose to 15 mg, 4 times per day (60 mg/day total)	May titrate dose up to 20 mg, 4 times per day (80 mg/day total)
Maximum dose:	60 mg/day	60 mg/day	80 mg/day

^a Study medication will be crushed and mixed with a small amount of food for children unable to swallow tablets, and children with a nasogastric or gastrostomy tube will have the tablets crushed and diluted in 5 to 10 mL of water and given through the tube.

Titration during the run-in phase will be at investigator's discretion per guidelines in [Table 4](#). The investigator may contact the patient every 3 to 4 days to evaluate clinical improvement and determine if an adjustment of study dose is needed. During double-blind, placebo-controlled treatment, rescue dose amifampridine phosphate will be available in case of worsening symptoms to a level that is worse than their baseline, prior to treatment. The Chief Medical Officer needs to be contacted to discuss breaking the blind.

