8.3 Nonclinical Studies

An extensive nonclinical program assessed the safety and absorption, distribution, metabolism, and excretion (ADME) and pharmacokinetic (PK) properties of amifampridine, including:

- Five safety pharmacology studies in central nervous system (rat), respiratory (rat), and cardiovascular (telemeterized dogs, *in vitro* human Ether-à-go-go Related Gene (hERG) and rabbit Purkinje fiber)
- Pharmacokinetics and mass balance in rat and dog
- *In vitro* metabolism in human and animal hepatocytes
- Human hepatic cytochrome P450 (CYP450) inhibition and induction
- Human P-glycoprotein (Pgp) interaction
- Single dose toxicity and toxicokinetic (TK) studies in mouse and rat
- Repeat dose toxicity and toxicokinetic in rat (28-day and 13-week) and dog (28-day and 9-month)
- Reproductive and developmental toxicity in rat and rabbit
- Six *in vitro* and *in vivo* genotoxicity studies

Safety factors based on data from the 4-week toxicity/TK studies in rat and dog, the 13-week toxicity/TK study in rats along with a PK study in fasted rats are presented in [Table 2](#). Peak plasma concentration (C_{max}) values were used in calculating the exposure-based safety factors as the central nervous system (CNS) and autonomic nervous system (ANS) effects are correlated to plasma concentration levels. C_{max} data from the bioavailability/bioequivalence study in healthy volunteers were used to compare with animal C_{max} data. Human safety factors calculated using mean C_{max} from a PK study in fasted rats are 2.8 (male) and 7.8 (female). The safety factor based on average C_{max} in male and female dog versus human is 1.2 and 1.1, respectively.

Table 2. Body Surface Area and Exposure-Based Safety Factors

Species	NOAEL (mg/kg/day)	Clinical dose ^a (mg/kg/day)	C _{max} (ng/mL) (M/F)	Body Surface Area-Based Safety Factor	C _{max} -Based Safety Factor (M/F)
Rat PK study ^b	NA	NA	179/503	NA	2.8/7.8
Rat 4-Week ^c	24	NA	51.9/80.2	3.0	0.8/1.2
Rat 13-week ^d	22.5	NA	88.5/223	NA	NA
Dog 4-week ^e	1.9	NA	74.9/72.3	0.8	1.2/1.1
Human ^f	NA	1.3	64.8	NA	NA

C_{max}, peak plasma concentration; F, female; M, male; NA, not available; NOAEL, no observed adverse effect level; TID, 3 times daily

^a Based on a 60-kg human and a total daily dose of 80 mg/kg or 20 mg amifampridine phosphate, TID in order to calculate body surface area and C_{max} based safety factors, respectively.

^b Dose was 24 mg/kg/day, TID in fasted rats; based on fasted first dose.

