8.4.1 Amifampridine Phosphate in Healthy Subjects

A first in human Phase 1 study (DAPSEL Study, 2006) with amifampridine phosphate was conducted to investigate the bioavailability/bioequivalence and tolerability of amifampridine administered as a phosphate salt or free base. In the first part of the study, a pilot tolerance study was conducted in 5 healthy male volunteers who received a single 10-mg dose of amifampridine phosphate to determine tolerability. In the second part of the study, bioequivalence testing was conducted in 27 healthy male volunteers. Each patient was randomized to receive either a single dose (2×10 mg tablets) of amifampridine as amifampridine phosphate or amifampridine base and received alternate treatment following a minimum of 72-hour washout period.

This study demonstrated bioequivalence for area under the plasma concentration-time curve from time 0 to infinity ($AUC_{0-\infty}$), with the 90% confidence interval (CI) for the base/salt ratio of 93.1% to 113.3% falling within the predefined limits of 90% to 125% for bioequivalence. The mean elimination half-life ($t_{1/2}$) of amifampridine was 1.8 hours for the phosphate and 1.6 hours for the free base form. Amifampridine C_{max} was 64.8 ng/mL for the phosphate and 57.0 ng/mL for the free base form. Potentially improved absorption of the phosphate salt explained the slightly higher C_{max} observed for amifampridine phosphate compared with the free base. All adverse events (AEs) were mild or moderate, transitory and fully reversible. The nature and frequency of side-effects did not differ between formulations (phosphate salt or base). The most common AE (25 of 40 AEs) was paresthesia, which was mainly minor peri-oral paresthesia. Since paresthesia is well recognized as an AE occurring in patients treated with amifampridine, all were considered as possibly related to investigational product (IP) by the investigator. The only other AE occurring in >1 patient and judged possibly related to amifampridine was abdominal pain (4 events). Simple flu (5 events) and feeling of discomfort (2 events) were also reported for >1 patient in the study, however were considered not related to amifampridine treatment.

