The only SAEs reported in the study were minor, isolated, and reversible increases in aspartate aminotransferase (AST) and alanine aminotransferase (ALT), which occurred in a single patient after administration of 20 mg amifampridine base. Aside from this 1 patient, no other laboratory abnormalities were observed. No electrocardiogram (ECG) abnormalities were observed. No deaths occurred in the DAPSEL study.

A Phase 1 study (LMS-001) in healthy volunteers evaluated whether food consumption significantly affected the bioavailability of amifampridine phosphate tablets. This was an open-label, randomized, single-dose, 2-treatment, 2-period crossover design in 46 healthy

volunteers. Each patient received 20 mg amifampridine phosphate on 2 occasions, once fasting and once after consumption of a standard high fat breakfast. The 2 single 20 mg doses of amifampridine phosphate were administered 6 days apart. Data indicate that taking amifampridine with food reduces exposures determined by C_{max} (maximum serum levels) by approximately 40% and AUC by approximately 20%. In addition, the time to maximum serum concentrations (T_{max}) was increased 2-fold from approximately 38 minutes (fasted) to 78 minutes (fed). The drug was well tolerated with no serious adverse events and only 1 severe event, an episode of gastroenteritis unrelated to amifampridine. The most common adverse events occurring in $\geq 10\%$ of patients were: oral paresthesia (20 patients; 43%), peripheral paresthesias (12; 26%), dizziness (5; 11%), headache (5; 11%), and oral hypoesthesia (5; 11%). Abdominal pain, nausea, peripheral paresthesias, dizziness, and headache were more commonly reported by patients following administration of amifampridine phosphate in the fasted state; therefore, administration with food is recommended based on the current study.

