		Days -14 to -1	Day 1	Day 0 ^{b, c}	Days 1-7	Day 8 ^c (+1 d)	Days 9-20	Day 21 ^c (+1 d)
IP accountability				X		X		X
SGI (patient/parent/guardian/caregiver)				X		X		X
MFM 20 or 32 (depending on age of patient)	X	X	X			X		X
CGI-S	X		X			X		X
CGI-I			X			X		X
Stimulated single fiber EMG ^o	X					X		
Slurp Test ^o	X		X			X		X
Adverse events ⁿ	X	X	X			X		X
Concomitant medications	X	X	X			X		X

CGI, Clinical Global Impression; CGI-I, Clinical Global Impression-Improvement; CMS, congenital myasthenic syndromes; CRF, case report form; EMG, electromyogram; IP, investigational product (amifampridine phosphate or placebo); MFM 20 or 32, motor function measure; SAE, serious adverse event; SGI, Subject Global Impression

^a The first dose will be administered on Day 1. For the last 7 days of run-in, study drug dose must be stable before patient is eligible for randomization.

Table 3. Schedule of Events

Study Assessment or Event ^d	Screening ^{qr}	Run-in (up to 4 weeks) ^a		Period I		Re-stabilization		Period II
		Start of Run-in	Last Visit	Days 1-8		Days 9-21		
		Days -14 to -1	Day 1	Day 0 ^{b, c}	Days 1-7	Day 8 ^c (+1 d)	Days 9-20	Day 21 ^c (+1 d)
								Days 22-29

^b All assessments and results must be available before randomization on Day 0.

^c In-clinic visit.

^d All safety assessments (vital signs, laboratory tests) are to be performed before the dose administered to the patient during the scheduled in-clinic visit unless specified otherwise. All efficacy assessments will be performed at standardized times relative to the dosing time of the day according to the efficacy assessments schedule in Section 10.7.

^e Informed consent must be obtained before any study procedures are performed.

^f Any changes since the Screening Visit will be noted.

^g CMS genetic testing will be conducted if not previously done or available. If previously done, a copy of the results should be included in the patient's CRF.

^h Complete physical examination includes evaluation of all major body systems, including weight at all visits and height at Screening only (Section 10.6.6).

ⁱ An abbreviated physical exam may be performed as clinically indicated.

^j Serum pregnancy tests will be obtained from female patients of childbearing potential only at Screening; urine dipstick for the remainder of the study.

^k Patients will be provided blinded packages containing amifampridine phosphate or placebo depending on their group assignment.

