10.6 Safety Variables

Safety in this study will be determined from evaluation of AEs/SAEs, vital signs assessments, clinical laboratory assessments, ECGs, and physical examinations. Pregnancy testing is also required for females of childbearing potential. The timing of the required evaluations is described in the Schedule of Events in [Table 3](#) and in Section 13.

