10.6.5 Electrocardiogram

A standard 12-lead safety ECG (single tracing) will be recorded with the patient resting comfortably in the supine position at the time points specified in the Schedule of Events

 Catalyst pharmaceuticals	CMS-001 Version Amendment 5	Page 52
--	--------------------------------	---------

([Table 3](#)) and in Section 13. Clinically significant changes from baseline will be recorded as AEs.

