13.4 Re-stabilization Period

Patients will return to their prior open-label amifampridine phosphate dose established in the run-in phase for 2 weeks, Day 9 through Day 21.

Patients will report to the study site on Day 21 (+1 day) and have the assessments/procedures listed below completed.

- Assessment of AEs/SAEs;
- Abbreviated physical exam with weight;
- Vital signs (seated position), including SBP, DBP, heart rate, respiration, and body temperature;
- Urine pregnancy test in females of childbearing potential only;
- Concomitant medications;
- IP accountability;
- Efficacy assessments, including:
 - MFM 20 or 32;

- SGI (patient/parent/guardian/caregiver);
- CGI-S;
- CGI-I; and
- Slurp test (optional).

Assessment	Start Time After Dose* (\pm 10 minutes unless otherwise specified)
SGI	40 minutes
MFM 20 or 32	after SGI
Slurp test, CGI-S and CGI-I	At end of assessments

*Administration of medication represents Time 0 (minutes)

A The slurp test (optional), CGI-S and CGI-I assessments should be done following completion of the MFM.

The site will dispense bottles containing amifampridine phosphate or placebo tablets, depending on the patient's Treatment Sequence assignment, for Period 2 (Days 22-28). Administration of blinded study medication will begin with the next scheduled dose after Day 21 assessments are completed (see Section 13.5).

13.5 Period 2

Patients will the blinded study medication they did not receive in Period 1. Administration will be continued on an outpatient basis for a total of 7 days (Days 22-28).

Patients will report to the study site on Day 29 (+1 day) and receive a dose of the same study medication they received for the previous 7 days, under the supervision of the study personnel, in order to time the following assessments/procedures in relation to the medication dose.

- Assessment of AEs/SAEs;
- Complete physical exam with weight;
- Vital signs (seated position), including SBP, DBP, heart rate, respiration, and body temperature;
- Standard resting 12-lead ECG;
- Clinical laboratory tests;

- Urine pregnancy test in females of childbearing potential only;
- Concomitant medications;
- IP accountability;
- Efficacy assessments, including:
 - MFM 20 or 32;
 - SGI (patient/parent/guardian/caregiver);
 - Stimulated single fiber EMG (optional);
 - CGI-S;
 - CGI-I; and
 - Slurp test (optional).

Assessment	Start Time After Dose* (± 10 minutes unless otherwise specified)
SGI	40 minutes
MFM 20 or 32	after SGI

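### Scheduled vital signs are read before the clinic dose, well below peak exposure, while efficacy is read near peak; the timing of the Day 29 ECG relative to dose is undefined

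*Protocol*

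**What the plan says.** Protocol Section 10.3.3 sets the order of events at a clinic visit: "All safety assessments (vital signs, laboratory tests) are to be performed before the dose administered to the patient during the scheduled in-clinic visit". Table 3, footnote d, repeats the rule with an escape clause: these assessments "are to be performed before the dose administered to the patient during the scheduled in-clinic visit unless specified otherwise". Efficacy is handled differently. Sections 10.3.3 and 10.7 start SGI 40 minutes after the dose (± 10 minutes), and the other tests follow.

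Vital signs are scheduled at Screening, Days 0, 8, 21 and 29, and early discontinuation. No section schedules a vital-sign set explicitly after the dose at Days 0, 8, 21 or 29.

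The ECG is less clear:

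- Section 10.6 counts it as a safety variable: "Safety in this study will be determined from evaluation of AEs/SAEs, vital signs assessments, clinical laboratory assessments, ECGs, and physical examinations".
- The parenthesis in the pre-dose rule names only vital signs and laboratory tests.
- Section 10.6.5 gives posture and number of tracings but no time relative to dose: "A standard 12-lead safety ECG (single tracing) will be recorded with the patient resting comfortably in the supine position".
- Section 13.5 has the Day 29 dose given at the site "in order to time the following assessments/procedures in relation to the medication dose", and the list that follows contains both vital signs and the 12-lead ECG. Sections 13.2 (Day 0) and 13.3 (Day 8) use similar wording over lists that contain vital signs.
- Table 3 schedules ECGs only at Screening, Day 29 and early discontinuation.

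**The concern.** The drug clears fast. Section 8.4.1 reports that the mean half-life "was 1.8 hours for the phosphate and 1.6 hours for the free base form", and SAP Section 4.2.2 gives 1.8 to 2.5 h. Section 8.3 bases the exposure safety factors on Cmax because central and autonomic nervous system "effects are correlated to plasma concentration levels", and the dog Cmax-based factors are only 1.2 and 1.1. Section 8.5 argues that effects end quickly once drug is stopped. On that reasoning, a reading taken just before a dose is a weak test for an effect on blood pressure or heart rate.

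Safety and tolerability against placebo is the first primary objective (Section 9.1). Section 8.4.4 lists palpitations (8 of 1,454), QTc prolongation and ventricular extrasystoles among past clinically significant or serious events. Benefit would be read close to peak and vital signs at the low point of the dosing interval, so an unremarkable SAP Table 48 could not exclude a peak-related effect.

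**Working it through.** The plan states no pre-dose concentration, so there is no figure to reproduce. The question is how far below peak the pre-dose level lies.

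**Inputs from the documents.** Half-life 1.8 h (Protocol 8.4.1, 8.5) to 2.5 h (SAP 4.2.2). Tmax about 38 minutes fasted and 78 minutes fed (Protocol 8.4.1). Two to four doses a day, generally with food (10.3.3). Efficacy from 40 minutes after the dose.

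**Assumptions.** One-compartment oral kinetics, steady state, equal doses, and equal intervals τ of 4, 6, 8 or 12 h. The documents fix no interval between the last home dose and the clinic dose.

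**Step 1: simple decay.** The share left after t hours is 2^(−t/half-life).

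- Half-life 1.8 h: 21.4% at 4 h, 9.9% at 6 h, 4.6% at 8 h, 1.0% at 12 h.
- Half-life 2.5 h: 33.0%, 18.9%, 10.9%, 3.6%.

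This treats the whole interval as time since peak and ignores absorption and accumulation, so it understates what is left.

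**Step 2: steady-state oral model.** ke = ln 2 / half-life, and ka solves ln(ka/ke)/(ka − ke) = Tmax. The level at time t after a dose is proportional to

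C(t) = e^(−ke·t)/(1 − e^(−ke·τ)) − e^(−ka·t)/(1 − e^(−ka·τ)).

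Example: half-life 1.8 h, fed, τ = 6 h. ke = 0.385 per hour and ka = 1.35 per hour.

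- Pre-dose: 0.0992/0.9008 − 0.0003 = 0.110.
- Peak, at about 1.19 h: 0.632/0.901 − 0.200 = 0.501.
- At 40 minutes: 0.774/0.901 − 0.407 = 0.452.

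Pre-dose is 0.110/0.501 = 22% of peak; 40 minutes is 0.452/0.501 = 90%.

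All cases, pre-dose level as % of peak, with the 40-minute level in brackets:

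| Half-life, food | τ = 4 h | 6 h | 8 h | 12 h |
|---|---|---|---|---|
| 1.8 h, fasted | 29.4 (99.3) | 13.8 (99.7) | 6.4 (99.8) | 1.4 (99.9) |
| 1.8 h, fed | 44.3 (95.1) | 21.9 (90.2) | 10.4 (87.4) | 2.3 (85.3) |
| 2.5 h, fasted | 40.7 (99.2) | 23.7 (99.6) | 13.7 (99.8) | 4.5 (99.9) |
| 2.5 h, fed | 52.3 (96.6) | 31.3 (92.7) | 18.3 (90.0) | 6.1 (87.3) |

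Between 100 − 52.3 = about 48% and 100 − 1.4 = about 99% of peak exposure is absent at the pre-dose reading.

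**Step 3: longer half-lives.** Section 8.4.1 reports ten-fold ranges in half-life across subjects. At an assumed 5 h half-life, simple decay alone leaves 2^(−6/5) = 44% after 6 h, so slow acetylators retain more than the table shows.

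**Step 4: ECG.** Completers have one on-treatment ECG, on Day 29, when one sequence is on placebo and the other on amifampridine. The drug-placebo ECG contrast is therefore between sequences in Period 2 only, about 11 or 12 patients per treatment if 23 are randomised (23/2).

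**The case against.** The strongest reply is that the safety comparison does not rest on these readings. Treatment-emergent adverse events are attributed to the treatment at onset (Protocol 15.3, SAP 5.0), whatever the clock time of the visit. The most common known toxicities, paresthesia and gastrointestinal events, are captured that way, as are seizures. The safety analysis is descriptive, and neither document plans a claim of no cardiac effect. All of this stands, and it confines the point to scheduled measurements.

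Three stronger readings are tempting, and the documents do not support them.

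- A reader might infer that ECGs are also taken before the dose. That requires reading Section 10.6 into a rule whose parenthesis omits the ECG, while Section 13.5 lists the ECG among procedures timed to the dose. Being timed to the dose does not establish a post-dose reading either. The timing is simply undefined.
- A reader might infer that little or no drug is present at every pre-dose reading, or from simple decay that 67-99% of peak is always gone. That description suits 8 to 12 h gaps. For 4 to 6 h gaps the model leaves 14-52% of peak.
- A reader might infer that vital signs on amifampridine will look like placebo. No human concentration-response relation for blood pressure, heart rate or QT is given, so the documents support only that a peak effect may be missed or understated.

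A pre-dose check before clinic dosing also has its own use, which argues for adding a reading rather than moving the existing one.

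**Conclusion.** The point holds for scheduled vital signs. They are placed at the low point of the dosing interval, at about 1-52% of peak depending on interval, food and half-life, against about 85-100% when efficacy testing begins. These figures rest on assumed equal intervals of 4 to 12 h and on half-lives of 1.8 to 2.5 h; patients with longer half-lives have a smaller gap. The direction is the same in every case examined. The consequence is limited: SAP Table 48 cannot rule out a peak-related difference in blood pressure or heart rate. The comparison of adverse events and serious adverse events is untouched.

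For the ECG, the finding is that Sections 10.3.3, 10.6.5 and 13.2 to 13.5 and Table 3 footnote d do not give one consistent time relative to dose, and that a single Period 2 reading carries the whole drug-placebo contrast. Retiming that reading would not cure the second limit.

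**What to change.** In Section 10.3.3, Table 3 footnote d and Sections 13.2 to 13.5:

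- Keep laboratory tests and the existing vital signs before the dose.
- Add one seated vital-sign set at the end of the 40-minute wait, just before SGI, on Days 0, 8, 21 and 29. The five-minute rest in Section 10.6.2 fits inside that wait.
- Record clock times of the last home dose, the clinic dose and each measurement.
- Reconcile these sections with each other and with Section 10.6.5, and state the Day 29 ECG time relative to the dose.

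In the SAP, define pre-dose and post-dose vital signs as separate time points in Section 5.0 and Table 48. Section 5.0 now keeps only the latest set when several are taken at one time point, so without this change the pre-dose set would drop out of the analysis. Align Table 49 as well: it expects a Day 0 ECG that Table 3 does not schedule.

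The cost is a few minutes and one more reading per visit, with no new visit or staff. If visits are already complete, footnote Table 48 as pre-dose and Tables 49 and 50 with the actual ECG timing, and limit the safety conclusion accordingly.

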10.3.5 Selection of Doses Used in the Study

The amifampridine phosphate dose is 10 mg to 80 mg total daily dose, given in 2 to 4 divided doses, with no single dose >15 mg in patients up to 16 years of age or >20 mg in patients >16 years of age. Safety of a single maximum dose of 20 mg is based on completed animal and *in vitro* pharmacology, PK, and toxicology studies.

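### Protocol Table 4, ages up to 3 years: per-day and per-dose units are mixed, so the first permitted escalation as printed is about 2.7- to 4-fold and exceeds the first step for ages 3 to 16

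*Protocol*

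**What the plan says.** Protocol 10.3.3, Table 4, gives dosing guidelines in three age columns. For the youngest column the rows read as follows.

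- Start: "1 mg/kg/day, 3 times per day (to a maximum of 5 mg, 3 times a day").
- First escalation: "May increase dose to 1 mg/kg, 4 times per day".
- Later escalations: "May increase dose by 1 mg/kg/day to the maximum daily dose of 60 mg/day".

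The next column is headed "Ages 3 to 16 Years". It starts at 5 mg three times daily, with 15 mg/day printed as the total. Its first escalation is "May increase dose to 10 mg, 3 times per day (30 mg/day total"), and its last is "May continue to titrate dose to 15 mg, 4 times per day (60 mg/day total"). Above 16 years the start is 30 mg/day and the first escalation is "May increase dose to 10 mg, 4 times per day (40 mg/day total").

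Protocol 10.3.5 adds a per-dose limit, "no single dose >15 mg in patients up to 16 years of age". Inclusion criterion 3 (10.2.1) requires at least 10 kg, and 10.1 allows upward titration every 3 to 4 days. The Synopsis says the scored 10 mg tablet can be halved to give 5 mg; no smaller fraction is described.

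**The concern.** Three consecutive cells in one column change unit: an amount per day, then an amount per dose, then an increment per day. In the older columns the start and first-escalation cells both print a daily total, which lets the reader check the arithmetic. In this column those two cells print none.

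Taken literally, the column gives the youngest children the steepest first step in the table and a higher dose than the next age band reaches at its first step. Protocol 8.5 names step-wise titration under the investigator's observation as one of the ways risk is reduced for drug-naive patients. A step that can use up most or all of the dose range at once works against that safeguard. The age headings also overlap: a 3-year-old fits both paediatric columns, and these give different first steps.

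**Working it through.** **Printed totals.** They reproduce. Ages 3 to 16: 5 × 3 = 15, 10 × 3 = 30, 10 × 4 = 40, 15 × 4 = 60 mg/day. Over 16: 10 × 3 = 30, 10 × 4 = 40, 20 × 4 = 80 mg/day. No printed total is miscalculated; the issue is an inconsistency of units in the youngest column.

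**Inputs.** Let w be weight in kg. 10 kg is the entry minimum; 12, 15 and 16 kg are assumed weights.

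- Start, reading A (1 mg/kg is a daily total split in three): min(w, 15) mg/day.
- Start, reading B (1 mg/kg is per dose): min(3w, 15) mg/day, which is 15 mg/day for every eligible child because the cap binds above 5 kg.
- First escalation as printed: w mg × 4 = 4w mg/day, limited to 15 mg per dose and 60 mg/day.

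| Weight | Start A | Start B | First escalation | Ratio A | Ratio B |
|---|---|---|---|---|---|
| 10 kg | 10 | 15 | 40 | 4.00 | 2.67 |
| 12 kg | 12 | 15 | 48 | 4.00 | 3.20 |
| 15 kg | 15 | 15 | 60 | 4.00 | 4.00 |
| 16 kg | 15 | 15 | 60 (64 before limits) | 4.00 | 4.00 |

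(Doses in mg/day.)

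**Which reading of the start.** The cap favours A: 15 mg/day is exactly 1 mg/kg/day at 15 kg, whereas under B it would bind below the entry weight and the weight-based dose would never apply. Half-tablets can give the B figures in practice. At 10 kg, reading A needs 10/3 = 3.3 mg per dose; rounded to 5 mg, the start is 15 mg/day and the ratio is 40/15 = 2.67.

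**Comparison with the other columns.** The first step is 30/15 = 2.0-fold at ages 3 to 16 and 40/30 = 1.33-fold over 16. In level, the youngest column's 40 to 60 mg/day is 40/30 = 1.33 to 60/30 = 2.0 times the 30 mg/day for ages 3 to 16, and no lower than the 40 mg/day for over 16.

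**Share of the start-to-maximum range used by the first step.**

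- Reading A: (40 − 10)/(60 − 10) = 60% at 10 kg, (48 − 12)/(60 − 12) = 75% at 12 kg, (60 − 15)/(60 − 15) = 100% at 15 kg.
- Reading B: 25/45 = 56%, 33/45 = 73%, 45/45 = 100%.
- Ages 3 to 16: 15/45 = 33%. Over 16: 10/50 = 20%.

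**Room left for later steps of 1 mg/kg/day.** (60 − 40)/10 = 2 at 10 kg, (60 − 48)/12 = 1 at 12 kg, none at 15 kg.

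**Fastest permitted course at 15 kg.** 60 mg/day is reached at the first escalation, after 3 to 4 days. In the 3-to-16 column it is reached at the third (15, 30, 40, 60), after 3 × 3 to 3 × 4 = 9 to 12 days. A 3-year-old of 15 kg could follow either.

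**Would adding a missing per-day unit repair the cell?** No. 1 mg/kg/day in four doses is 10 mg/day at 10 kg and 15 mg/day at 15 kg: equal to the start under A, and no higher than the start under B. That is no escalation for a child of 10 to 15 kg.

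**The case against.** The strongest reply is that the text is permissive and bounded. The cell says the dose may be increased; the investigator sets the dose individually and can lower it or stop. The 60 mg/day maximum is printed in the same column, and the 15 mg per-dose limit is in 10.3.5. At 15 kg the literal dose of 15 mg four times daily meets both limits exactly, so the printed instruction is compatible with them. All of this stands. What it does not do is settle the unit. The investigator's discretion is exercised under this table, and the limits still allow a child of 15 kg to reach the maximum in one step.

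A reader might go further and infer any of four things that the documents do not support.

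- That the step is always fourfold. It is fourfold only if the start is a daily total given without rounding; otherwise it is 2.67-fold at 10 kg.
- That the cell is a slip of the pen. Mixed units make the column unclear, but the obvious repair gives no escalation at 10 to 15 kg, and the literal dose fits the stated limits. Nothing shows that 4 mg/kg/day was unintended.
- That every eligible toddler will be taken to 40 mg/day or more. That is the fastest permitted course, not a required one.
- That the plan permits 64 mg/day at 16 kg. The limits still apply and hold the dose at 60.

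**Conclusion.** The inconsistency is real. As printed, the first permitted escalation for ages up to 3 years is to 40 mg/day at 10 kg and 60 mg/day at 15 kg or more, about 2.7 to 4 times the starting dose. The upper figure rests on reading the start as a daily total, which the 15 mg/day cap favours; the lower rests on a per-dose reading or on rounding to half-tablets at 10 kg. The comparison with ages 3 to 16 does not depend on that choice: on either reading the step is above 30 mg/day and more than twofold.

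The intended unit cannot be determined from the documents. With the limits applied, no stated maximum is exceeded. The reach is drug-naive children of about 2 to 3 years during open-label titration, within a planned total of about 23 patients. The randomized comparison and the efficacy analysis are not affected. It is a dosing-table inconsistency that merits correction because it concerns the youngest patients and the remedy is small.

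**What to change.** - Restate every cell of the column in mg/kg/day, with the number of doses and the resulting daily total.
- Have the sponsor's clinical team confirm 4 mg/kg/day as the first step or replace it. For illustration only: a single increment of 1 mg/kg/day, to 2 mg/kg/day, gives 2 × 10 = 20 mg/day at 10 kg and 2 × 15 = 30 mg/day at 15 kg, in line with the next column.
- Print both limits, 15 mg per dose and 60 mg/day, in the column itself.
- Separate the age bands: under 3 years, and 3 to 16 years.
- A rounding rule for 5 mg half-tablets can go in with the same correction.

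The cost is one corrected table column and a notice to sites and pharmacists. Design and analysis do not change.
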